9.5	Cumulative incidence of medically attended RTI	13
9.6	Cumulative incidence of RTI related hospital admission	13
9.7	Cumulative incidence of pneumonia diagnosed by a GP or medical specialist	13
9.8	Mental, physical and social functioning at 6 months	13
9.9	Serious adverse events and adverse events	13
9.10	Cumulative incidence of all-cause 6-month mortality.....	14
10	Analysis of the exploratory endpoints	15
10.1	Interaction between BCG and other vaccines.....	15
10.2	Immunological endpoints (conditional on funding)	15
11	References.....	16

1 List of abbreviations

ADL:	Activities of Daily Living
BCG:	Bacillus Calmette-Guérin
CI:	Confidence interval
COVID-19	Corona Virus Disease 2019: Disease associated with infection with SARS-CoV-2 (please refer to the study definition in section 3.3)
crRTI	Clinically relevant respiratory tract infection
SARS-CoV-2	Severe acute respiratory syndrome coronavirus-2: The virus that causes COVID-19
eCRF:	electronic Case Report Form
ICU:	Intensive Care Unit
IQR:	Inter Quartile Range
RCT:	Randomised Controlled Trial
SD:	Standard deviation
UMCU:	University Medical Center Utrecht
VAS:	Visual Analogue Scale

2 Overview of the study

This is a copy of the protocol summary, version 2.1, 12-Nov-2020:

Rationale: On March 11 2020 the World Health Organization (WHO) declared the coronavirus (SARS-CoV-2) outbreak a pandemic. Worldwide, the number of confirmed cases continues to rise, leading to significant morbidity and mortality. In the Netherlands, although the incidence is currently low due to social distancing measures, recurrence of infections is expected once measures are going to be lifted. Although individuals of any age can acquire SARS-CoV-2, adults of middle and older age are at highest risk for developing severe COVID-19 disease. Moreover, recent reports demonstrate that mortality rates rise significantly among patients 60 years and older. Therefore, strategies to prevent SARS-CoV-2 infection or to reduce its clinical consequences in vulnerable populations are urgently needed. Bacille Calmette-Guérin (BCG) vaccine not only protects against tuberculosis, but also induces protection against various respiratory infections, including those with a viral etiology. We hypothesize that BCG vaccination reduces clinically relevant respiratory tract infections requiring medical intervention, including COVID-19, in vulnerable elderly.

Objective: To determine the impact of BCG vaccination on the incidence of clinically relevant respiratory infections or COVID-19 in vulnerable elderly.

Study design: An adaptive multi-center double-blind randomized placebo-controlled trial.

Study population: 5,200 to 7,000 vulnerable elderly, defined as ≥ 60 years of age and being discharged from hospital in the last 6 weeks, having a chronic somatic comorbidity, undergoing major surgery, or attending a thrombosis care service. Patients with contraindications to BCG vaccination as stipulated in the Summary of Product Characteristics (SPC) and patients with a history of COVID-19 will be excluded.

Intervention: Participants will be randomized between intracutaneous administration of BCG vaccine (Danish strain 1331) or placebo (0.1ml 0.9% NaCl) in a 1:1 ratio.

Main study parameters/endpoints: The trial has an adaptive primary endpoint. Based on accrual of the two endpoints, the primary endpoint will be either (a) COVID-19 or (b) clinically relevant respiratory tract infection (RTI) requiring medical intervention, potentially including COVID-19 episodes. The other will be declared secondary endpoint. Other secondary endpoints include: all SARS-CoV-2 infections (including asymptomatic infections), influenza infection, RTI (all infections regardless of medical intervention), RTI-related hospital admission, COVID-19 related hospital admission, pneumonia, mental, physical and social functioning, serious adverse events and adverse events, and death.

Nature and extent of the burden and risks associated with participation, benefit and group relatedness: Based on previous experience in published and ongoing randomized controlled trials in adults and elderly, the risks of BCG vaccination are considered negligible. Vaccination could cause local pain, suppuration and scarring at the site of injection. The size of the trial will ensure rapid availability of results that can inform policy-making during the ongoing pandemic and may be of benefit for participants that received no intervention, as well as individuals who did not participate in the trial.

3 Sample size

This is an event driven trial. To demonstrate a 50% reduction of the incidence of the primary endpoint with a two-sided alpha of 0.05, 67 endpoints are needed for 80% power and 90 events for 90% power.

Two candidate primary endpoints are selected: COVID-19 and clinically relevant RTI. For the primary endpoint COVID-19 we consider 80% acceptable given the high need for a fast answer to whether BCG is efficacious. For clinically relevant RTI 90% power is selected. The final primary endpoint will be selected based on the accrual of number of endpoints.

Given the urgent medical need, we consider a sample size of 7,000 to provide the optimal balance between number of participants and expected duration of the trial, while a sample size of 5,200 would be minimally acceptable. For a detailed sample size calculation, please refer to the protocol.

4 Definitions

4.1 Treatment groups

BCG: participants randomised to receive BCG

Placebo: participants randomised to receive placebo

4.2 Analysed populations

The primary analysis population is the intention-to-treat (ITT) population in which participants will be analysed according to the random allocation.

Subgroups:

We will explore the presence of interaction between BCG and other vaccines, in particular influenza and pneumococcal vaccine.

4.3 Study definitions

COVID-19 disease is defined as respiratory tract symptoms and/or systemic symptoms in combination with detection of SARS-CoV-2 in a respiratory sample.

SARS-CoV-2: severe acute respiratory syndrome coronavirus-2. The virus that causes COVID-19 disease.

crRTI: clinical symptoms of a respiratory tract infection in combination with the need for medical intervention. (See protocol for a detailed definition.)

5 General statistical considerations

5.1 General statistical methodology

The methodology presented in this statistical analysis plan takes into account methods planned in the protocol, specifies them, and completes them. The analysis will be performed in the statistical software R.(1) The version of R and R libraries used will be reported.

5.2 Handling of missing data

For analyses of primary or secondary endpoints with missing data, multiple imputed data analysis will be performed using Multivariate Imputation by Chained Equations; complete data analysis will be performed as a sensitivity analysis to check for inconsistencies.(2) Missing outcome data will not be imputed.

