6.2 Conduct of the study

The following will be reported on the conduct of the study:

- Enrolment period: date First Patient First Visit – date Last Patient First Visit
- Distribution of actual duration of follow-up per participant by treatment arm
- Number and proportion of days with missing outcome measurement by treatment arm (e.g. due to dropout or noncompleted questionnaires)

7 Demographics and other baseline characteristics

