The primary study parameter will be analyzed as a time-to-event outcome using a Cox proportional hazards analysis. The randomization date will be considered T=0 and the symptom onset date of the primary endpoint (or in case of COVID-19 the date of positive test result if that occurs earlier) will be considered the event time. Censoring time of participants with no event will be the last date of follow-up. The analysis will be adjusted for the stratification variables (hospital and age category) and for strong prognostic factors*. The result will be reported as the number of episodes per arm, number of patient-years of follow-up per arm, and hazard ratio (HR) with 95% CI.

* For COVID-19 there are no prognostic factors that can be measured at enrolment so only stratification variables will be used. For clinically relevant RTI: presence of the following (groups of) comorbidities: cardiovascular disease or stroke, chronic pulmonary disease (COPD, asthma or other chronic pulmonary disease), diabetes mellitus, solid organ or hematological malignancy, moderate to severe chronic renal disease.

9 Analysis of the secondary endpoints

Please refer to the protocol for definitions of each endpoint.

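### Is the planned missing-data sensitivity analysis empty for COVID-19, and does it leave missing outcome days untested?

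*SAP*

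**What the plan says.** Section 5.2 has three parts. It sets the method: "For analyses of primary or secondary endpoints with missing data, multiple imputed data analysis will be performed", by chained equations. It names one sensitivity analysis: "complete data analysis will be performed as a sensitivity analysis to check for inconsistencies". It then sets a limit: "Missing outcome data will not be imputed".

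Section 8 fixes the primary Cox model. On covariates it says "The analysis will be adjusted for the stratification variables (hospital and age category") plus strong prognostic factors, with an exception: "For COVID-19 there are no prognostic factors that can be measured at enrolment so only stratification variables will be used". For clinically relevant RTI it adds five comorbidity groups. On risk time it says "Censoring time of participants with no event will be the last date of follow-up", and it asks for the "number of patient-years of follow-up per arm".

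Sections 9.1–9.7 and 9.10 reuse the COVID-19 analysis. Section 9.8 regresses change scores on arm with hospital and age category as covariates. Section 9.9 uses logistic regression and names no covariate. Section 10.1 stratifies by baseline influenza and pneumococcal vaccination status.

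Section 6.2 lists among the items to be reported: "Number and proportion of days with missing outcome measurement by treatment arm (e.g. due to dropout or noncompleted questionnaires").

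**The concern.** Read together, these sections seem to promise a robustness check that checks nothing for the endpoint needing the fewest events. If outcomes are never imputed and the only covariates are the randomisation strata, the imputed and complete-data fits are one calculation. A report could then say that the missing-data sensitivity analysis agreed with the main result when it could not have done otherwise.

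The missing data that 6.2 foresees are outcome days lost to dropout or skipped questionnaires, and the comparison does not reach them for any endpoint. Section 8 neither defines the last follow-up date nor says whether uncovered days before it stay in the risk set. Two analysts could treat those days differently and report different patient-years and confidence intervals. Section 5.4 ties significance to the 95% CI, so the verdict could depend on that choice.

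**Working it through.** **Step 1. What can be imputed in each model?** Inputs: 5.2 (outcomes excluded) and the covariates named in sections 8, 9 and 10.

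| Analysis | Covariates besides arm | Anything to impute? |
|---|---|---|
| COVID-19 (8) | hospital, age category | no |
| 9.1–9.7, 9.10 | as COVID-19 | no |
| 9.9 | none named | no |
| 9.8 | hospital, age category; outcome is change from a self-reported baseline | only if a missing baseline score is not counted as outcome data |
| Clinically relevant RTI (8) | strata plus five self-reported comorbidity groups | yes |
| 10.1 | stratified by self-reported vaccination status | yes |

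The pair therefore coincides for COVID-19 and for nine of the ten section 9 headings, and for 9.8 on one of two readings. A simulated trial (6,000 participants, an assumed 10% of comorbidity values missing) shows this. The COVID-19 model gave HR 0.497 from both analyses. The RTI model gave 0.509 on complete data (5,415 participants) and 0.494 after imputation, so there the comparison is a real one.

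**Step 2. The plan's event counts.** Section 3 gives 67 and 90 events for a 50% reduction at two-sided 0.05. Schoenfeld's formula, 4(z₀.₉₇₅ + z_power)²/(ln 0.5)², gives 65.3 and 87.5, rounded up to 66 and 88. Both are within two of the stated counts, and the present question does not affect them.

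**Step 3. Can uncovered days bias the hazard ratio?** Let m be the share of follow-up days uncovered in an arm (mB for BCG, mP for placebo) and r the share of gap-day episodes that are nevertheless recorded. The SAP gives neither; all values are assumptions. With gap days kept at risk, the HR is multiplied by

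[1 − mB(1 − r)] / [1 − mP(1 − r)].

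- Equal gaps: exactly 1.
- 12% against 10%, r = 0: 0.88/0.90 = 0.98.
- 20% against 10%: r = 0.8 gives 0.96/0.98 = 0.98; r = 0.5 gives 0.90/0.95 = 0.95; r = 0 gives 0.80/0.90 = 0.89.

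A material bias needs clearly unequal gaps together with poor later capture. The trial is double-blind, and 6.2 would show unequal gaps by arm.

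**Step 4. Can the choice change the verdict when gaps are equal?** Take d recorded episodes and true HR 0.5, so that BCG's share of episodes is 0.5/1.5 = 1/3. Each episode falls on an uncovered day with probability q = mr/(1 − m + mr). Compare z = ln(HR)/√(1/dB + 1/dP), where dB and dP are the episodes in each arm, with and without those episodes.

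| m, r | q | Verdicts differ, d = 67 | Verdicts differ, d = 90 |
|---|---|---|---|
| 5%, 0.5 | 0.026 | 4% | 2% |
| 10%, 1 | 0.10 | 8.7% | 5.6% |
| 20%, 1 | 0.20 | 14.8% | 10.3% |

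At d = 67, the change is from significant to non-significant in 6.9 of the 8.7 points and 12.8 of the 14.8. Power falls from about 79.5% to 74.4% and 68.8%. That is what happens when 10% or 20% of known events are thrown away; it does not show that keeping them is wrong. When no gap-day episode is recorded (r = 0), the verdict almost never differs: 0.1%, from a run with m = 10% and no true effect.

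Patient-years with gap days in exceed those with gap days out by m/(1 − m): 5%, 11% and 25% for m = 5%, 10% and 20%.

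**Step 5. Would a start-stop analysis help?** Such an analysis removes uncovered days from the risk set. Suppose gaps are equal at 10%, reports are missed twice as often in the illness week, and there is no true effect. At r = 0 the placebo event rate is then 20% too low in the main analysis and 11% too low with start-stop. At r = 0.5 it is 10% and 12% too low. The HR is 1.00 in both throughout.

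**The case for a change.** The strongest case for a change needs no assumed rates. A SAP exists to fix choices such as the last date of follow-up and the handling of intermittent gaps, and this one says that it specifies and completes the protocol's methods. A sensitivity analysis that must agree with the main analysis could be misreported as reassurance, and correcting the text would be cheap.

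Part of this stands. The overlap is real, and 5.2 would be clearer if it said that imputation concerns covariates only and whether baseline scores in 9.8 are included. The rest does not carry. Section 5.2 calls for the pair only where data are missing; with nothing to impute, the natural course is to run one analysis and report no agreement. It never claims to test outcome days, only to look for inconsistencies. Section 8 gives the time origin, the event date and the censoring date, so on its plain reading time at risk runs to the last follow-up date and recorded episodes count. Declining to impute missing outcomes removes neither days nor recorded events. Reporting intervals, recall periods and other outcome sources commonly belong in the protocol, which is not at hand. If a later report or record covers a gap, section 8's rule is right as it stands.

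**Conclusion.** The observation is correct, but it does not call for a change. The imputed and complete-data analyses coincide for COVID-19 and for 9.1–9.7, 9.9 and 9.10, and for 9.8 unless baseline scores are imputed. The consequence is an inactive general clause, not a wrong result. The clause does its work in the clinically relevant RTI model, which is a candidate primary endpoint, and in 10.1.

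No error in the primary hazard ratio is shown. With equal gaps the bias factor is 1, and the multipliers of 0.98 to 0.89 need unequal gaps of which the SAP gives no sign. The differing verdicts (4% to 14.8% at 67 episodes, 2% to 10.3% at 90) rest on assumed values of m and r and, in the two larger cases examined, mostly reflect lost power. A start-stop analysis would leave the HR as it is, would not reliably improve the event rate, and would discard recorded episodes in an event-driven trial. An analyst can fill the remaining gap sensibly: impute covariates only, follow the protocol for the last follow-up date, keep all recorded first episodes, and report the 6.2 table beside the result without presenting the imputation comparison as evidence about missing outcome days.

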5.3 Descriptive statistics

According to the variable type, descriptive statistics will be:

- Quantitative criteria: number of observations (N), mean, standard deviation (SD), median and inter-quartile range (IQR), as applicable.
- Qualitative criteria: number of observations (N), absolute frequency (n) and relative frequency (%). Percentages will be calculated on the number of participants with documented data.

5.4 Inferential statistics

Effect estimates for primary and secondary endpoints will be reported with 95% CI. Effect estimates with a 95% CI not including the zero-effect will be considered statistically significant.

6 Disposition of participants and conduct of the study

6.1 Participant disposition and size of the analysed populations

The study flowchart will describe:

- Number of subjects screened
- Number of subjects not meeting the eligibility criteria
 - o Reasons for non-eligibility
- Number of subjects eligible but not included
 - o Reasons for non-inclusion
- Number of participants included and randomised
- Early termination: Number of participants withdrawn, dropouts
 - o Reasons for early termination

6.2 Conduct of the study

The following will be reported on the conduct of the study:

- Enrolment period: date First Patient First Visit – date Last Patient First Visit
- Distribution of actual duration of follow-up per participant by treatment arm
- Number and proportion of days with missing outcome measurement by treatment arm (e.g. due to dropout or noncompleted questionnaires)

7 Demographics and other baseline characteristics

7.1 Demographics / baseline characteristics

The following data will be described for included participants by treatment arm and for the total population:

VARIABLE	DERIVATION	STATISTICAL METHOD *
Age (years)	Self-reported at baseline	Median (IQR) or mean (sd) ¹
Gender	Self-reported at baseline: Male/ Female	n/N (%)
History of BCG vaccination	Self-reported at baseline: Yes/No	n/N (%)
Age at BCG vaccination	Self-reported at baseline	Median (IQR) or mean (sd) ¹ among those with reported history of BCG vaccination
BMI	Self-reported at baseline	Median (IQR) or mean (sd) ¹
Receipt of influenza vaccination in past season (2019-2020 or 2020-2021 depending on date of enrolment)	Self-reported at baseline: Yes/No	n/N (%)
Receipt of pneumococcal vaccination in past or current season	Self-reported at baseline: Yes/No	n/N (%)
Receipt of other vaccinations in past 12 months	Self-reported at baseline (open question) ²	n/N (%) for each reported vaccination
History of hypertension	Self-reported at baseline: Yes/No	n/N (%)
History of cardiovascular disease	Self-reported at baseline: Yes/No	n/N (%)
History of stroke	Self-reported at baseline: Yes/No	n/N (%)
History of diabetes mellitus	Self-reported at baseline: Yes/No	n/N (%)
History of COPD	Self-reported at baseline: Yes/No	n/N (%)
History of asthma	Self-reported at baseline: Yes/No	n/N (%)
History of other pulmonary diseases	Self-reported at baseline: Yes/No and open question ²	n/N (%) for each reported pulmonary disease if deemed relevant
History of moderate to severe renal disease	Self-reported at baseline: Yes/No	n/N (%)
History of solid organ or haematological malignancy	Self-reported at baseline: Yes/No	n/N (%)
History of dementia (diagnosed by physician)	Self-reported at baseline: Yes/No	n/N (%)
History of other chronic diseases	Self-reported at baseline: Yes/No and open question ²	n/N (%) for each reported disease if deemed relevant
Medication use	Self-reported at baseline	Listing of medication on group level based on ATC code system
Clinical Frailty Scale	Self-reported at baseline	Median (IQR)

History of smoking	Self-reported at baseline. Options are: - Never smoked - Ever smoked - Current smoking	n/N (%) for all categories
Smoking of household member	Self-reported at baseline: Yes/No	
Alcohol use	Self-reported at baseline: Yes/No, quantity in categories	n/N (%) per category
History of allergic rhinitis	Self-reported at baseline: Yes/No	n/N (%)
Other allergies	Self-reported at baseline: Yes/No and free text	n/N (%) per category if deemed relevant
Type of home	Self-reported at baseline: - Independent - Sheltered 11ccommodation - Care home - Nursing home	n/N (%) per category
Presence of household members	Self-reported at baseline: Yes/No	n/N (%)
Education level	Self-reported at baseline, categories	n/N (%) per category
Payed work	Self-reported at baseline: - Yes - Unemployed, searching for a job - Unemployed, not actively searching - Retired	n/N (%) per category
Working environment	Self-reported at baseline: - Patient care - Day-care - Primary or secondary school - Vocational education or highschool - None of the above	n/N (%) per category
Receives domestic help by indication	Self-reported at baseline: Yes/No	n/N (%)
Receives home care	Self-reported at baseline: Yes/No	n/N (%)
Dependence in ADL	Self-reported at baseline: Katz-ADL, Lawton IADL	Median (IQR) or mean (sd) ¹
Quality of life / utilities	Self-reported at baseline, EQ5D3L	Median (IQR) or mean (sd) ¹
Health status	Self-reported at baseline, VAS	Median (IQR) or mean (sd) ¹

* It will not be statistically tested whether baseline characteristics differ by treatment arm.

1. The description method will depend on the normality of the data.
2. Open questions will be categorized by the coordinating investigator.

8 Analysis of the primary endpoint

The trial has an adaptive primary endpoint. Based on accrual of primary endpoints the primary endpoint will be selected as soon as one of the candidate primary endpoints has reached the required number of episodes. The non-selected candidate primary endpoint will be analysed as secondary endpoint.

The two primary endpoints concerned are: (see protocol chapter 7 for definitions)

- a) COVID-19 (67 episodes for 80% power)
- b) Clinically relevant RTI (90 episodes for 90% power)

Only first episodes per participant will be considered.

The primary study parameter will be analyzed as a time-to-event outcome using a Cox proportional hazards analysis. The randomization date will be considered T=0 and the symptom onset date of the primary endpoint (or in case of COVID-19 the date of positive test result if that occurs earlier) will be considered the event time. Censoring time of participants with no event will be the last date of follow-up. The analysis will be adjusted for the stratification variables (hospital and age category) and for strong prognostic factors*. The result will be reported as the number of episodes per arm, number of patient-years of follow-up per arm, and hazard ratio (HR) with 95% CI.

* For COVID-19 there are no prognostic factors that can be measured at enrolment so only stratification variables will be used. For clinically relevant RTI: presence of the following (groups of) comorbidities: cardiovascular disease or stroke, chronic pulmonary disease (COPD, asthma or other chronic pulmonary disease), diabetes mellitus, solid organ or hematological malignancy, moderate to severe chronic renal disease.

9 Analysis of the secondary endpoints

Please refer to the protocol for definitions of each endpoint.

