9.10 Cumulative incidence of all-cause 6-month mortality

Analysis will be the same as for the primary endpoint COVID-19.

10 Analysis of the exploratory endpoints

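### The all-cause mortality model in SAP 9.10 takes over a covariate set chosen for COVID-19, leaving out age in years and frailty, which the SAP collects; the test is valid and the power loss small

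*SAP*

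**What the plan says.** Section 8 sets one covariate rule for the primary Cox model: the two stratification variables plus strong prognostic factors. The footnote then differs by candidate endpoint. Clinically relevant RTI receives five comorbidity groups. COVID-19 receives nothing further: "For COVID-19 there are no prognostic factors that can be measured at enrolment so only stratification variables will be used".

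Section 9.10, on all-cause 6-month mortality, consists of one sentence: "Analysis will be the same as for the primary endpoint COVID-19". Its covariates are therefore hospital and age category.

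Section 7.1 lists what is recorded at baseline. This includes age in years, the "Clinical Frailty Scale", a range of comorbidities and, among the functional measures, ADL scores. The rationale copied into section 2 states that "mortality rates rise significantly among patients 60 years and older".

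**The concern.** The footnote shows that covariates were meant to be chosen endpoint by endpoint. For death no choice is visible. The endpoint receives the COVID-19 set through a cross-reference, and the only reason given for that set is that COVID-19 has no predictor measurable at enrolment. That reason says nothing about death, for which age and frailty are obvious candidates that the SAP already holds.

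Precision on a secondary endpoint is at stake. In a Cox model, leaving out a covariate that predicts the event moves the treatment hazard ratio towards 1 while its standard error hardly changes, so some power is lost. The loss grows with the strength of the predictor and the frequency of the event.

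**Working it through.** **1. The SAP's own figures.** Section 3 says that, for a 50% reduction, "with a two-sided alpha of 0.05, 67 endpoints are needed for 80% power and 90 events for 90% power". Schoenfeld's formula with 1:1 allocation is d = 4(z₁₋α/₂ + z₁₋β)² / (ln HR)².
- 80% power: 4 × (1.960 + 0.842)² / 0.4805 = 65.3, so 66 events. The SAP has 67, which gives 81.0%.
- 90% power: 4 × (1.960 + 1.282)² / 0.4805 = 87.5, so 88 events. The SAP has 90, which gives 90.8%.

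These figures reproduce to within two events. They concern the primary endpoint. The SAP gives no expected number of deaths and no power for mortality.

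**2. Assumptions for death.** Control mortality, mortality HR and the SD of the baseline log-hazard (the strength of the predictors) are not in the SAP and are varied below. Sample sizes lie within the planned 5,200 to 7,000.

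**3. Predictors measured without error.** Simulation with 6,000 participants, 1:1, follow-up to 6 months and 1,200 trials per scenario. The model with a two-level age category is compared with one using continuous age and a frailty/comorbidity index. The two-level category is itself an assumption.

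| Control mortality, HR | Deaths | SD 0.7 | SD 1.0 | SD 1.4 |
|---|---|---|---|---|
| 1%, 0.5 | about 45 | 61.7 → 61.8 | 60.1 → 60.8 | 59.0 → 60.8 |
| 2%, 0.6 | about 95 | 69.1 → 68.5 | 69.2 → 69.9 | 65.7 → 68.5 |
| 4%, 0.7 | about 190–200 | 71.4 → 72.0 | 69.6 → 71.2 | 65.9 → 70.1 |

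Entries are power in %, age category only → with the added covariates. The Monte Carlo SE of the difference is 0.4 to 0.9 points. The change runs from about 0 to 4 points.

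**4. Where the gain comes from.** In the last cell (189 deaths) the mean HR is 0.707 without and 0.693 with the covariates. Approximate power is Φ(½√d × |ln HR| − 1.960):
- 0.707: ½√189 × 0.347 − 1.960 = 0.42, so 66%.
- 0.693: ½√189 × 0.367 − 1.960 = 0.56, so 71%.

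This is close to the simulated 65.9% and 70.1%. The shift in the HR accounts for the gain.

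**5. Predictors measured imperfectly.** Simulation with 5,200 participants, HR 0.70 and 1,000 trials per scenario. Age is assumed to explain 36% of the log-hazard variance, and measured frailty to correlate 0.6 with true frailty.

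| Control mortality, SD | Planned | Imperfect predictors | Perfect score |
|---|---|---|---|
| 6%, 1.6 | 74.0% | 77.8% | 84.1% |
| 6%, 1.2 | 75.7% | 78.1% | 81.7% |
| 2%, 1.2 | 37.2% | 36.7% | 37.5% |
| 1%, 1.2 | 21.5% | 21.8% | 21.7% |

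The SE of one power estimate near 75% is √(0.75 × 0.25 / 1,000) = 1.4 points. A further simulation with imperfect predictors gave 73% to 78% (6%, SD 1.6), 81% to 82% (6%, SD 1.2) and no clear gain at 2% to 4%. Absolute levels differ between the simulations, so only the contrast within each should be read. With imperfect predictors the gains are 3.8, 2.4, −0.5 and 0.3 points in the table, and 5 and 1 points at 6% in the further simulation: about 0 to 5 overall.

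**6. Primary endpoint.** With 7,000 participants, about 68 COVID-19 events, HR 0.5 and SD 1.2, power is 77.1% with the planned model and 78.2% with added covariates.

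**The case against.** The strongest reply is that nothing here is invalid. Adjusting a randomised comparison for its stratification variables alone is a standard, prespecified choice, and this is a secondary endpoint. That stands, and it limits the point to efficiency and consistency. It does not supply a reason for the covariate set, and section 8 shows that the authors wanted strong prognostic factors in the primary model where they exist.

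Five stronger readings are tempting, and the SAP does not support them.
- **The SAP asserts that death has no prognostic factors.** It does not. The footnote is confined to COVID-19, and 9.10 borrows an analysis, not a reason. Narrowing the footnote to symptomatic disease would change nothing, because section 4.3 already requires symptoms.
- **The mortality HR is biased.** Hazard ratios are non-collapsible. The less-adjusted and more-adjusted HRs are different quantities, and neither is an error.
- **Power falls by about 10 points.** One scenario gives 75% against 85%, but it needs 6% mortality, SD 1.6 and a near-perfect risk score. For a rare event, SD 1.6 implies an AUC of Φ(1.6/√2) = 0.87, while section 7.1 relies on self-report.
- **Age is missing, or its categories are coarse.** Age category is in the model, and the SAP does not give its cut-points. Only the finer information in age in years is lost.
- **The rationale proves that age predicts all-cause death here.** The sentence in section 2 is about COVID-19, and all participants are at least 60. It makes the assumption plausible and no more.

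**Conclusion.** The point holds as a minor one. Section 9.10 gives all-cause death a covariate set whose stated justification applies only to COVID-19, while age in years and the Clinical Frailty Scale are collected and unused. The planned test keeps its validity.

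The cost is about 0 to 5 points of power, towards the upper end only with strong predictors and control mortality near 6%, and near zero when deaths are few. The range rests on assumed mortality of 1% to 6%, assumed hazard ratios of 0.5 to 0.7 and assumed predictor strength, none of which the SAP states. That age and frailty predict death in this population is also assumed. A reader might infer that the 80% power for the primary COVID-19 endpoint is in doubt. It is not, since the difference there is about 1 point.

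**What to change.** In 9.10, replace the cross-reference with a Cox model adjusted for hospital, age category, age in years and Clinical Frailty Scale. Fix this list before unblinding and keep it whatever the number of deaths. A rule that drops covariates when deaths are few would make the model depend on the outcome and would be less firm than the present text. Because the cross-reference also carries the time axis, the new sentence should say that time runs from randomisation to the date of death. Leave the section 8 footnote unchanged.

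The cost is one short SAP edit, two more model terms, and imputation of missing baseline values under section 5.2. No new data are needed. If deaths are few, little is gained.
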